APPENDIX 2. IMMUNE-RELATED RESPONSE EVALUATION CRITERIA IN SOLID TUMORS

Conventional response criteria may not be adequate to characterize the antitumor activity of immunotherapeutic agents, which can produce delayed responses that may be preceded by initial apparent radiographic progression, including the appearance of new lesions. Therefore, immunotherapy-specific response criteria adaptations to RECIST 1.1 ([Eisenhauer et al 2009](#)) have been developed to allow for unconventional response and progression patterns. These include modified RECIST 1.1 for immune-based therapeutics (iRECIST; [Seymour et al 2017](#)), which was developed by the RECIST working group in an effort to create a common set of criteria that the cancer immunotherapy field could apply to clinical trials.

Response evaluation through use of iRECIST requires collection of tumor assessment data after radiographic progression per RECIST 1.1. Details regarding lesion evaluation are described below. When not otherwise specified, RECIST 1.1 conventions will apply.

Criteria for determining overall response at a single time point per iRECIST are also summarized below. Of note, overall response per iRECIST will not be captured in the eCRF, but will instead be calculated programmatically by the Sponsor on the basis of Investigator-assessed individual lesion data recorded in the eCRF.

iRECIST response status is not a specific component of treatment discontinuation criteria, including decisions about whether to continue treatment beyond progression per RECIST 1.1. Investigators should instead take into account radiologic data and clinical status in making such decisions.

Evaluation of Lesions to Support IRECIST Response Assessment after Disease Progression per RECIST 1.1

iRECIST is an extension of RECIST 1.1 that allows for response assessment following disease progression per RECIST 1.1. RECIST 1.1 rules for categorizing lesions as measurable or nonmeasurable and measuring lesions (see [Appendix 1](#)) also apply to iRECIST. After disease progression per RECIST 1.1, the same target and nontarget lesions selected at baseline will continue to be followed, along with any new lesions that develop, to support iRECIST response evaluations, as described below and summarized in [Table 22](#). Once a lesion has been categorized as a target, nontarget, or new lesion, it will remain classified as such.

Target Lesions

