The target lesions selected at baseline should continue to be measured at all tumor assessment time points after disease progression per RECIST 1.1, according to RECIST 1.1 conventions.

Nontarget Lesions

Nontarget lesions selected at baseline should continue to be followed at all tumor assessment time points after disease progression per RECIST 1.1. At each time point, nontarget lesions should continue to be categorized as “absent” (complete response [CR]), “unequivocal progression” relative to baseline (progressive disease [PD]), or “present without unequivocal progression” (non-CR/non-PD), as defined by RECIST 1.1. In addition, any nontarget lesions that were categorized as PD at the previous time point should be evaluated to determine whether there has been any further increase in size.

New Lesions

New lesions identified after baseline will be evaluated for measurability with use of the same criteria applied to prospective target lesions at baseline per RECIST 1.1 (e.g., nonlymph node lesions must be ≥ 10 mm on the longest diameter; new lymph nodes must be ≥ 15 mm on the short axis [see note below]). All new lesions (measurable or nonmeasurable) must be assessed and recorded at the time of identification and at all subsequent tumor assessment time points.

Up to a maximum of 5 measurable new lesions total (with a maximum of two lesions per organ) should be selected and measured at each time point. New lesions that are not measurable at first appearance but meet measurability criteria at a subsequent time point should be measured from that point on, if the maximum number of measurable new lesions has not been reached.

However, for calculation of the sum of diameters for new lesions, iRECIST excludes measurements from new lesions that were not measurable at first appearance.

All nonmeasurable new lesions (including those that subsequently become measurable) and additional measurable new lesions (in excess of 5 total or two per organ) should be assessed to determine whether there is any increase in size relative to the previous assessment time point.

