screening, then end of even-numbered cycles, cycle 2, 4 and additional cycles, and within 14 days after last dose at end of treatment/early termination visit.

- RECIST v1.1 will be used to determine response for patients with solid tumors. The response categories of target lesions include complete response (CR), partial response (PR), stable disease (SD), progressive disease (PD), and not evaluable (NE). The response categories of non-target lesions include: CR, Non-CR/Non-PD, and PD. The appearance of new malignant lesions denotes disease progression. An overall response will be summarized taking all target lesion, non-target lesion, new lesion into consideration.
- iRECIST is an extension of RECIST 1.1 that allows for assessment of response in patients being treated with immunotherapeutic agents. Overall response per iRECIST will be captured in the eCRF. According to iRECIST (protocol appendix 2), target lesions, non-target lesion and new lesion will be continually measured per RECIST response criteria after disease progression. For patients who are assessed as PD by RECIST (Target or Non-target lesions), they will perform repeated response assessments by RECIST and the response will be collected according to the eCRF. If the repeated assessments show PD again, the patients are confirmed as PD in the first assessment. If the repeated assessments show CR, PR or SD, the patients are not confirmed as PD. The appearance of any new lesions is considered as disease progression per RECIST 1.1.
- LYRIC evaluates response in patients with lymphoma who are being treated with immunotherapeutic agents. The response of lymphoma will be assessed separately for CT-based assessment and PET-CT based assessment. CT-based assessment includes complete radiologic response, partial remission, stable disease, progressive disease, immune response 1, immune response 2, immune response 3 and not evaluable. PET-CT based assessment includes complete metabolic response, partial metabolic response, no metabolic response, progressive metabolic disease, immune metabolic response 1, immune metabolic response 2, immune metabolic response 3 and not evaluable. Combined Overall Response includes complete response (CR), partial response (PR), stable disease (SD), progressive disease (PD), immune response 1 (IR1), immune response 2 (IR2), immune response 3 (IR3), and not evaluable (NE).

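### SAP section VII.A.1 takes the iRECIST response from the eCRF, against protocol Appendix 2, and its repeat-by-RECIST rule confirms progression for any new lesion that persists

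*SAP*

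**What the plan says.** **Source of the iRECIST response.** SAP section VII.A.1 (Assessment Method): "Overall response per iRECIST will be captured in the eCRF". Protocol Appendix 2: "overall response per iRECIST will not be captured in the eCRF, but will instead be calculated programmatically by the Sponsor", working from the lesion data that the Investigator enters. The SAP cites Appendix 2 in its very next sentence.

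**Confirmation in SAP VII.A.1.** The repeat is triggered by RECIST PD in target or nontarget lesions. For these patients, "they will perform repeated response assessments by RECIST and the response will be collected according to the eCRF". Then: "If the repeated assessments show PD again, the patients are confirmed as PD in the first assessment". And: "If the repeated assessments show CR, PR or SD, the patients are not confirmed as PD". The same bullet ends: "The appearance of any new lesions is considered as disease progression per RECIST 1.1".

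**Confirmation in SAP VII.A.3 (time-to-event endpoints).** Here the repeat is judged against the iRECIST criteria. Separate rules cover progression that is not confirmed, patients who are not clinically stable, and patients with no repeat scan.

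**Lesion follow-up in protocol Appendix 2.** A new lesion keeps that classification. Up to 5 measurable new lesions are measured at each time point, and the remaining new lesions are checked for growth since the previous assessment. For nontarget lesions already called PD, the parallel instruction is that they "should be evaluated to determine whether there has been any further increase in size".

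**Use.** SAP VII.A.2 summarizes best overall response and ORR separately for RECIST, iRECIST and LYRIC. ORR is a secondary objective; TTP and PFS are exploratory. The RECIST 1.1/iRECIST response table (Table 11 in SAP Appendix 5) is planned for both interim analyses.

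**The concern.** There are two problems in one SAP bullet. First, a programmer cannot follow both documents on where the iRECIST response comes from. If the eCRF was built as Appendix 2 describes, the field the SAP relies on is not there.

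Second, Appendix 2 adopts iRECIST because immunotherapy can produce late responses after apparent progression, and it names new lesions as one form of that progression. A rule that re-applies RECIST at the repeat scan asks only whether the new lesion is still there, not whether it has grown. The measurements of new lesions that Appendix 2 requires then play no part in confirmation. At stake is whether the iRECIST columns can show anything that the RECIST columns do not, for the patients in whom the two were expected to differ.

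**Working it through.** The plan gives no figure to reproduce. The check compares the texts and then runs the SAP rule through the protocol's own response table.

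**1. Source.**

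| | SAP VII.A.1 | Protocol Appendix 2 |
|---|---|---|
| Overall iRECIST response | recorded in the eCRF | not recorded in the eCRF |
| Origin | eCRF entry | Sponsor program on lesion data |

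Both statements cannot hold.

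**2. Repeat scan under Table 21 (protocol Appendix 1).** Inputs: 5 target states (CR, PR, SD, PD, not all evaluated) and 4 nontarget states (CR, non-CR/non-PD, not all evaluated, PD), so 5 × 4 = 20 combinations. Any PD component or any new lesion gives overall PD. SAP VII.A.1 is then applied: PD confirms; CR, PR or SD does not.

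| New lesion at repeat | PD | CR | PR | SD | NE |
|---|---|---|---|---|---|
| Still present | 20 | 0 | 0 | 0 | 0 |
| Gone | 8 | 1 | 5 | 3 | 3 |

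The second row arises as follows.
- PD: 4 combinations with target PD, plus 4 with nontarget PD and another target state, = 8.
- CR: target CR with nontarget CR = 1.
- PR: 2 from target CR with nontarget not CR and not PD, plus 3 from target PR, = 5.
- SD: 3.
- NE: 3. One of these, with both target and nontarget lesions incompletely evaluated, has no row in Table 21 and is read here as NE.

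These are counts of logical combinations, not probabilities.

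**3. Reading the result.**
- *Lesion persists:* PD is confirmed in 20 of 20, including target CR with nontarget CR. Suppose the targets have shrunk by 30% or more (PR) and the new lesion is unchanged. The patient is confirmed as progressed and dated to the first scan, exactly as under RECIST.
- *Lesion has gone:* 1 + 5 + 3 = 9 of 20 give CR, PR or SD, so PD is not confirmed and iRECIST can differ from RECIST.
- *Repeat is NE:* 3 of 20. VII.A.1 gives no rule.

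**4. VII.A.1 against VII.A.3.** One section confirms by RECIST, the other by the iRECIST criteria. For a persisting, non-growing new lesion these need not agree, and the SAP does not say which applies.

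**5. Is the algorithm written anywhere?** Appendix 2 announces criteria for the iRECIST response at a time point. The text that follows, including Table 22, gives only instructions for evaluating lesions. Neither document sets out the rule that the program would need.

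**6. Scale.** The documents give no rate of new-lesion progression or of persistence, so the number affected cannot be calculated. As an illustration, take one patient moved between non-responder and responder. On 20 patients the ORR shifts by 1/20 = 5.0 points. On 34 (the 20 expansion patients plus a dose level filled to its maximum of 14) it shifts by 1/34 = 2.9 points. With the exact 90% interval that SAP VII.A.2 plans for the Arm 2 RP2D cohort, moving from 0 to 1 responder raises the upper limit from 13.9% to 21.6% at n = 20, and from 8.4% to 13.2% at n = 34. Both denominators assume that every patient is in the iRECIST analysis.

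**The case against.** Several points on the other side stand and set the limits of this one.

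- A reader might infer that iRECIST equals RECIST whenever progression is a new lesion. The documents do not support that: if the lesion has resolved by the repeat scan, 9 of 20 combinations leave PD unconfirmed. The broad statement would hold only if new-lesion PD is never sent for repeat. The trigger, which names target and nontarget lesions, allows that reading but does not state it. For a lesion that persists, either reading gives PD.
- A reader might infer that delayed responses are lost altogether. ORR counts PR or CR at any time on study, so a response after an earlier PD still counts if no new lesion persists. Only responses that occur while a new lesion is still present are at risk.
- A reader might infer that the TTP and PFS dates are wrong. They are governed by VII.A.3, which invokes the iRECIST criteria, and their planned tables are titled by RECIST 1.1 and LYRIC. What can be said is that the two sections disagree.
- The phrase about further increase in size in Appendix 2 concerns nontarget lesions. The growth check for new lesions is a separate instruction and covers nonmeasurable and excess lesions; measurable new lesions are measured.
- The eCRF is not available, and the SAP plans an iRECIST listing (19.1), so the field may exist. The SAP is based on protocol version 4.0, while the version of the supplied protocol cannot be read. The rules for starting Arm 2 also differ between the two documents, so a version mismatch is plausible. That might explain the contradiction, but it does not resolve it.

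It is also fair that efficacy is descriptive and that Appendix 2 keeps iRECIST status out of the treatment discontinuation criteria.

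**Conclusion.** The point holds in this form. The SAP and protocol contradict each other on the source of the iRECIST response. The confirmation rule in VII.A.1 gives PD again for every new lesion that persists (20 of 20 combinations), whatever the other lesions do and whether or not the new lesion has grown. VII.A.3 describes confirmation differently. This is more than missing detail: a stated rule gives a result at odds with the purpose for which Appendix 2 adopts iRECIST.

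Affected are best overall response and ORR by iRECIST and, if VII.A.1 is followed, the progression dates for TTP and PFS. The primary DLT endpoint and the lymphoma patients assessed by LYRIC are not affected. The conclusion assumes that Table 21 is applied unchanged at the repeat scan, as the instruction to repeat by RECIST implies. Whether a given patient with shrinking targets and a stable new lesion would count as an iRECIST responder depends on an algorithm that neither document writes out.

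**What to change.** 1. Reconcile the source. Bring SAP VII.A.1 and protocol Appendix 2 to one statement, with the iRECIST overall response derived by program from the recorded lesion data, as Appendix 2 says. If the eCRF does hold an Investigator iRECIST field, say what it is used for.
2. Replace the repeat-by-RECIST rule in VII.A.1 with a written iRECIST time-point and confirmation algorithm in which a new lesion that merely persists does not by itself confirm progression. Cover new lesions that grow, persist or resolve, and a repeat assessment that is NE. State whether PD from a new lesion alone triggers the repeat. A reference to Appendix 2 is not enough, because the algorithm is not there.
3. Use the same algorithm in VII.A.1 and VII.A.3.

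The cost is SAP wording and derivation code. Appendix 2 already requires the lesion data, so no new assessments are needed. The change should precede the interim analyses in which the iRECIST response table is due.

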10^6 , 1×10^7 , 3×10^7 , 1×10^8 , 3×10^8 , and 1×10^9 live cells will be explored independently. A de-escalation dose of 3×10^5 live cells is available if the starting dose is deemed not tolerable. All dose escalation and de-escalation decisions will be based on the occurrence of DLTs at a given dose during Cycle 1 and will be made jointly by the Investigators and the Sponsor. If the initial eligible lesion undergoes complete regression and is no longer injectable, subsequent eligible lesions (until no more eligible lesions remain) may be injected. At the end of Cycle 4, patients may receive additional cycles of SYNB1891; for details refer to protocol section 4. The dose selected as achieving the target DLT range will be considered the MTD.

After determination of the MTD in Arm 1, dosing will begin in Arm 2 at a 10-fold lower dose than the Arm 1 MTD and will be increased in approximately 3-fold increments in subsequent cohorts until RP2D determination. Patients will follow the same four 21-day cycles schedule as Arm 1 and SYNB1891 will be administered by i.t. injection into an eligible lesion on Days 1, 8, and 15 of Cycle 1 and Day 1 of Cycles 2 through 4. In addition, atezolizumab will be administered in accordance with its recommended dose and schedule (1200 mg IV Q3W) on Day 1 of each of the 4 planned cycles. Combination doses will not be escalated above the SYNB1891 single-agent MTD established in Arm 1. On days when atezolizumab and SYNB1891 are both administered, SYNB1891 will be administered first, followed by at least 1 hour of observation prior to the atezolizumab infusion. Patients in Arm 2 who do not have progressive disease at the end of Cycle 4 on combination therapy may receive additional cycles of SYNB1891 and atezolizumab for up to 24 months, details refer to protocol section 4.

Once the RP2D of Arm 2 is determined, up to 20 additional patients may be enrolled in the RP2D cohort to fully characterize the safety profile of SYNB1891 in combination with atezolizumab.

B. Study Population

This study comprises patients with advanced/metastatic solid tumors or lymphoma. Patients will be eligible for enrollment regardless of gender or race/ethnicity. Additional inclusion and exclusion criteria can be found in protocol section 5.

C. Sample Size Predictions

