For records with a missing procedure date, the following procedure will be employed for use in determining whether the procedure is prior or concomitant:

- Procedure dates with a missing day and non-missing month will be assumed to occur on the first day of the non-missing month, except for

- procedures occurring in the month of first dosing, in which case the date will be the date of first dosing.
- Procedure dates with missing day and month will be assumed to occur on the first day of the non-missing year (i.e., January 1), except for procedures occurring in the year of first dosing, in which case the date will be the date of first dosing.

For records with a missing disease progression date from prior therapy, the following procedure will be employed for use in analyzing time to event endpoints:

- If the disease progression date is completely missing OR only the year is available, set as missing.
- If both year and month of disease progression date from are available and only day is missing, the date of disease progression will be imputed by the last day of the month.

For records with a partial death date, the following procedure will be employed for use in deriving time to event variables.

- The death date will be imputed by the earliest possible date that is not contradicting with any other available data in the database.

All other data will be reported as they are collected. No imputation methods will be used to replace missing data unless otherwise stated in this document.

D. Interim Analyses

This is a single-arm, open-label study, so interim analyses may be performed as the study progresses.

Details of analysis will follow each section described in this SAP, may including the following components:

- Disposition
- Protocol deviations
- Baseline characteristics: demographics, disease history, medical history, concomitant medication/procedure
- Key components from efficacy analysis
- Key components from safety analysis
- PK and pharmacodynamic data (as available)

E. Analysis Populations

1. Safety Population

The safety population includes participants who were enrolled, allocated to treatment, and received at least one dose of investigational product.

2. Efficacy Population

The efficacy population includes participants who received study drug and had an on-treatment response assessment (including “Not Evaluable”) or who discontinued study before any response assessment performed due to disease progression.

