3. PK/Pharmacodynamic Population

The PK/PD population includes participants who received study drug and had at least one PK or PD assessment.

F. Data Display Characteristics

All analyses will be performed using SAS statistical analysis software. Descriptive statistics for continuous variables will include the number of patients, arithmetic mean, standard deviation (SD), median, minimum, and maximum. Geometric mean and geometric coefficient of variation (geoCV) may be used for PK/PD analyses. Summary statistics for categorical variables will contain count and percentage based on the number of patients in a cohort and the selected analysis population. Percentages will be presented to one decimal, except for one hundred percent, which will be presented as 100%.

Data displays produced for this study will include three types: summary tables, data listings and figures. Unless stated otherwise, data listings will be produced for all recorded data. Data listings will list the data recorded on the eCRF or obtained from external vendor for each patient. They will be ordered by arm, dose level, site, subject number, and time of assessment. When expedient, additional levels of ordering hierarchy may reflect subsets of assessments within an individual patient. Data listings will not display patient initials. Additional data listings may be produced for outcome measures that involve extensive procedures to derive the analyzed outcomes.

Summary tables will be produced as specified in following sections. Summary tables will display summary statistics calculated for each arm, dose cohorts and all patients combined, unless described otherwise in the following sections. For most summary tables, the arm and dose group will be presented in a column and the summary statistics of interest will be presented in rows.

Efficacy analysis will be summarized according to the planned dosing schedule. Safety analysis will be summarized according to the actual dosing schedule. For patients who were assigned a wrong study dose, they would be recoded in protocol deviation and dosing compliance; if the wrong dose occurred only once, the safety analysis will use the patients’ initial planned dose as summary cohorts. If more than one wrong dose occurred, the safety analysis will use patients’

actual dose as summary cohorts. If patients' doses were reduced, safety analysis will use the initial planned dose as summary cohorts.

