Patients’ best overall response will be selected based on the overall response order (CR, PR, SD, PD, NE for RECIST; CR, PR, SD, PD, IR1, IR2, IR3 for LYRIC) through the study. Objective Response Rate (ORR), defined as the proportion of patients’ overall response achieving a PR or CR at any time on the study, will be summarized descriptively by arm and cohort. In addition, an exact 90% confidence interval (CI) will be presented for RP2D cohort in Arm 2. Note that the definition of the Efficacy Population includes all treated patients who have an on-treatment response assessment or who discontinued study early due to disease progression; therefore, all Efficacy Population patients will be included in the denominators for percentage even if the patient had a Not Evaluable response. The best overall response and objective response rate will be summarized separately for each assessment method (RECIST, iRECIST, or LYRIC).

Similarly, the proportion of patients with a PR and the proportion of patients with a CR at any time during the study will be summarized as part of the best

overall response. The sum of diameters and change from baseline will also be summarized, by arm and cohort at each assessment visit.

All overall tumor and lymphoma response data will be presented in patient listings.

3. Determination of Time to Event Endpoints

Below is a list of events definitions for the solid tumor patients with a confirmed response according to RECIST v1.1 and iRECIST, and lymphoma patients with response according to LYRIC. The number of events and the number of censored patients will be summarized. The median time to event (reported in days) and the 25th and 75th percentiles on the time to event for each arm and cohort will be summarized using Kaplan-Meier estimates. Progression-Free Survival graphs will also be provided.

When calculating the endpoint that involve PD diagnosis date, such as time to progression or progression free survival, below rules will apply to account for the repeated PD response assessment per iRECIST:

- When a patient has disease progression per RECIST, if the repeated assessment confirmed as disease progression according to iRECIST criteria, the first PD date will be used in the endpoint calculation.

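### Method-specific response rates have no method-specific denominator: read literally, SAP VII.A.2 counts lymphoma patients as RECIST non-responders and solid-tumor patients as LYRIC non-responders

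*SAP*

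**What the plan says.** Four parts of the SAP bear on this.

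- **Who is studied and who is analyzed.** Section III.B: "This study comprises patients with advanced/metastatic solid tumors or lymphoma". The Efficacy Population (V.E.2, same in Protocol 10.1) is one pooled set: "The efficacy population includes participants who received study drug and had an on-treatment response assessment", or who left the study earlier because of progression. It has no tumor-type subset.
- **Which method applies to whom.** Section VII.A.1: "RECIST v1.1 will be used to determine response for patients with solid tumors". iRECIST is described there as an extension of RECIST 1.1. For lymphoma, "LYRIC evaluates response in patients with lymphoma who are being treated with immunotherapeutic agents".
- **The denominator and the split.** Section VII.A.2 says that "all Efficacy Population patients will be included in the denominators for percentage even if the patient had a Not Evaluable response". The next sentence reports BOR and ORR by method. Before both, it promises an exact 90% confidence interval for the RP2D cohort in Arm 2.
- **General rule and table list.** Section V.F bases categorical summaries on "count and percentage based on the number of patients in a cohort and the selected analysis population". Appendix 5 gives the analysis population of Table 11 (RECIST 1.1/iRECIST) and Table 12 (LYRIC) simply as Efficacy.

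A restriction to the patients to whom a method applies is written once, in VII.A.3, for one set of spaghetti plots. Nothing similar is written for ORR.

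**The concern.** No patient can be a responder under both systems. If both tumor types enroll in a cohort and each method-specific rate is divided by the whole cohort, every lymphoma patient lowers the RECIST and iRECIST rates and every solid-tumor patient lowers the LYRIC rate, whatever their actual outcomes. The same applies to the BOR percentages.

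ORR is a stated secondary endpoint, and Tables 11 and 12 are marked for both interim analyses, so the effect would recur. The smaller group suffers most: a LYRIC rate over the whole cohort mainly reflects how few lymphoma patients there were. An interval computed on that denominator would also suggest far more information about lymphoma than exists.

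**Working it through.** The plan states no ORR, target rate or interval width, so there is no figure of its own to reproduce. The check is what the written denominator does.

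**Inputs.** The denominator is all Efficacy Population patients in the cohort (SAP VII.A.2, V.F). The interval is exact 90%, taken here as two-sided Clopper-Pearson. Protocol 4.2.3 allows 3 to 14 patients at a dose level and up to 20 more at the RP2D, so a fully expanded RP2D cohort would hold 3 + 20 = 23 to 14 + 20 = 34. The number of lymphoma patients and all responder counts are assumptions, because the documents give neither. N = 20 is used as a round illustration.

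**Algebra.** Let N be the Efficacy Population patients in the cohort, L of them with lymphoma, with r_S solid-tumor and r_L lymphoma responders.

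- RECIST, literal: r_S/N = [r_S/(N−L)] × (N−L)/N, so at most (N−L)/N.
- LYRIC, literal: r_L/N = [r_L/L] × L/N, so at most L/N.

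The shrinkage factors depend only on the tumor mix. With N = 20 and L = 2 they are 18/20 = 0.90 and 2/20 = 0.10.

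**Numbers, N = 20 and L = 2 (exact 90% interval):**

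| Assumed result | Literal denominator | Tumor-type denominator |
|---|---|---|
| 4 RECIST responders | 4/20 = 20.0% (7.1–40.1) | 4/18 = 22.2% (8.0–43.9) |
| 2 LYRIC responders | 2/20 = 10.0% (1.8–28.3) | 2/2 = 100% (22.4–100) |
| 0 LYRIC responders | 0/20 = 0% (0–13.9) | 0/2 = 0% (0–77.6) |

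The last row shows the precision problem: no response in two lymphoma patients would appear to rule out rates above 13.9%, when the two patients leave anything up to 77.6% open. The intervals are shown for both methods only to display the effect; whether the SAP intends them by method is taken up below.

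**Range for RECIST, 4 responders.** At N = 20, the understatement runs from 4/19 − 4/20 = 21.1% − 20.0% = 1.1 points (L = 1) to 4/14 − 4/20 = 28.6% − 20.0% = 8.6 points (L = 6). At N = 34 it runs from 4/33 − 4/34 = 0.4 points to 4/28 − 4/34 = 2.5 points. At L = 0 it is zero.

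**The case against.** The sentence in VII.A.2 is about Not Evaluable patients. It explains that they stay in the denominator because of how the Efficacy Population is defined, and it does not mention tumor type. Keeping them is conventional and is not in question. The surrounding text links each method to a tumor type, Table 12 is titled as a lymphoma table, and the waterfall plots use the measure that fits the patient's cancer. The authors may well have meant tumor-type denominators. V.F is a generic display convention, and naming Efficacy as the population does not forbid a subset. The separate table shells, which are not available here, may carry the right counts. Response data are also listed by patient, so a reader of the full report could recompute any rate.

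The argument about intent stands, and it limits how strongly the point can be put. It does not remove it: no sentence gives the ORR denominator by method, the one sentence that addresses it says all, and V.F and the table list point the same way. Where the authors wanted only applicable patients, in the spaghetti plots, they said so.

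A reader might go further and infer that both method-specific rates are bound to be biased downward, or that the RP2D interval is computed on the wrong n. The documents support neither. The first depends on both tumor types enrolling in the same cohort and on a literal reading. As for the second, the interval is introduced before the split by method and is never said to be method-specific. It may belong to one combined ORR with each patient classified by the applicable criteria, and for that the pooled n is correct.

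**Conclusion.** Wrong as written, and easily corrected. Followed to the letter, in a cohort with both tumor types, the SAP divides each method-specific BOR and ORR by patients whom that method cannot assess. The RECIST and iRECIST rates shrink by the factor (N−L)/N and the LYRIC rate by L/N. With few lymphoma patients the RECIST loss is small and the LYRIC loss is large. These sizes rest on assumed lymphoma and responder counts; only the two caps follow from the text alone. The mismatch lies between RECIST/iRECIST and LYRIC, not between RECIST and iRECIST, which share the same patients. For the RP2D interval the finding is only that its ORR and denominator are unspecified. Efficacy is descriptive, no decision threshold is attached to ORR, and dose decisions rest on Cycle 1 DLTs, so neither the primary analysis nor escalation is affected.

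**What to change.** Amend SAP VII.A.2 to say three things:

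1. For each method-specific BOR and ORR, the denominator is the Efficacy Population patients with the tumor type that the method assesses (solid tumor for RECIST and iRECIST, lymphoma for LYRIC), Not Evaluable patients included.
2. The full Efficacy Population is the denominator only for a combined ORR, if one is presented, with each patient classified by the applicable criteria.
3. Which ORR, and which denominator, the exact 90% interval for the RP2D cohort uses. An interval for every method is optional.

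Tables 11 and 12 in Appendix 5 and their shells should carry the matching subset counts. The cost is a few sentences and table footnotes; no new data, visits or assessments are needed.
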